6.4. Covariates and Subgroups

The protocol does not define any formal subgroup analyses, and the study is not adequately powered to perform subgroup analyses.

6.5. Missing Data and Outliers

All attempts will be made to collect all data per protocol. As missing data are expected to be minimal, no imputation will be performed for missing values. Any data point that appears to be erroneous or inexplicable based on clinical judgment will be investigated as a possible outlier. If data points are identified as outliers, sensitivity analyses will be performed to examine the impact of including or excluding the outliers. Any substantive differences in these analyses will be reported. Non-analyzable data will be documented in the deviations.

6.6. Protocol Safety Review Team (PSRT)

No formal interim analyses involving hypothesis testing were planned. The analyses described here are for safety review only, by the PSRT.

A PSRT will be established by PATH to monitor the study and to provide independent, non-binding advice on safety and ethics. The PSRT will be composed of the Principal Investigator, the PATH Medical Officer and the Independent Research Monitor who will periodically review the conduct and safety of the study. The PSRT will be supported by an unblinded secretary and an unblinded biostatistician, both from Emmes. The responsibilities and procedures of the PSRT are defined in the PSRT Charter.

Three blinded reviews of data will be conducted by the PSRT when safety, reactogenicity and clinical lab data from all subjects in a cohort are available up to 7 days post-dose 3 of the study vaccine. Each report will be provided to the PSRT for their review to determine whether the study can continue to enroll for the next, dose-escalating cohort or whether the study should be stopped. At the time of each interim analysis, PATH will neither have access to the individual treatment assignments, nor to any unblinded safety reports (if applicable), but will be provided with aggregated safety results per cohort to allow strategic decisions for the future of the study.

The following summaries will be generated by group and all analyses will be performed on the safety population. Each PSRT report will be based on a unique frozen data base.

1. Occurrence of solicited local AEs during a 7-day follow-up period (i.e., on the day of vaccination and 7 subsequent days) after the first, second and third dose.
2. Occurrence of solicited systemic AEs during a 7-day follow-up period (i.e., on the day of vaccination and 7 subsequent days) after the first, second and third dose.
3. Occurrence of unsolicited AEs after each dose and up to 28 days after the third dose (dose intervals are 21 days).
4. Occurrence of hematological (red blood cell, white blood cell, differentials, hematocrit, platelet count and hemoglobin) and biochemical (Sodium, Potassium, Glucose, AST, ALT, BUN and Creatinine) laboratory abnormalities within 7 days of each dose.
5. Occurrence of SAEs at any time during the study at the time of data freeze.

6.7. Multiple Comparisons/Multiplicity

Due to the early clinical trial phase and the exploratory nature of this study, no adjustment for multiplicity will be performed.

7. STUDY SUBJECTS

7.1. Disposition of Subjects

Table 7 will present a summary of the reasons that subjects were screened but not enrolled. The composition of analysis populations, including reasons for subject exclusion, by study group, will be presented in **Table 8**. The disposition of subjects and receipt of study vaccinations will be tabulated by study group for all subjects. Summary of subject disposition will include number of subjects screened, enrolled, receiving study product, completing the study, and with immunogenicity results available (**Table 9**). A CONSORT diagram of the study will also be prepared (**Figure 1**).

A listing of subjects who discontinued vaccinations or terminated from study follow-up and the reason will be included in **Listing 1**.

7.2. Protocol Deviations

A summary of subject-specific protocol deviations will be presented by the deviation category, deviation type, and study group for all subjects (**Table 3**). All subject-specific protocol deviations and non-subject-specific protocol deviations will be included as data listings (**Listing 2** and **Listing 3**). Protocol deviations will not necessarily always lead to exclusion from the Immunology analysis population.

8. SAFETY EVALUATION

Safety is the primary objective of this study. Continuous measures will be assessed using mean, standard deviation, median, and range; categorical measures will be assessed using frequencies and proportions with exact 95% CIs. For safety assessments presented by time point, unscheduled assessments will be summarized as separate time points in chronological order with scheduled study visits.

All safety analyses will be based on the safety population and presented by treatment group.

8.1. Demographic and Other Baseline Characteristics

A summary table of continuous measures (age, height, weight) and categorical measures (gender, race, ethnicity) will be presented by treatment group and overall (**Table 10**). Demographic listing will also be prepared (**Listing 4**).

8.1.1. Prior and Concurrent Medical Conditions

All current illnesses and past pre-existing medical conditions will be MedDRA® coded using MedDRA dictionary version 20.1 or higher. Summaries of subjects' pre-existing medical conditions will be prepared (**Table 11**), and individual subject listings will be prepared for all pre-existing medical conditions (**Listing 5**).

8.1.2. Prior Medications

A summary of medications that were taken strictly prior to dosing will be presented by WHO Drug Classification ([Table 12](#)). Individual subject data will be included in the listing prepared for all concomitant medications ([Listing 14](#)).

8.2. Measurements of Treatment Compliance

A summary of the number of doses of study product administered to subjects will be prepared as part of the subject disposition table ([Table 9, Appendix A](#)).

8.3. Adverse Events

The primary objective of this study is safety of the Invaplex_{AR}-DETOX vaccination. All summaries of adverse events will be presented by vaccine dose (1 to 3) and overall, and by treatment group. Safety summaries and analyses will be presented for the Safety Population.

Local and general (systemic) solicited AEs, as well as lymph node assessments, are collected within 30 minutes of each vaccine dose and through 7 days following each dose (day of vaccination and subsequent 7 days). Lymph nodes are assessed as palpable or not palpable and for tenderness (yes/no). All other solicited events and symptoms are graded as 0 (normal), 1 (mild), 2 (moderate), 3 (severe), and 4 (potentially life-threatening). All general and local reactions are listed below.

Local Reactions:

- Site pain, site tenderness, swelling, induration, site redness and pruritus.

General Reactions:

- Fever, nausea, vomiting, abdominal pain, diarrhea (loose stools), appetite change, fatigue, headache, myalgias, arthralgias and malaise.

Adverse events will be summarized by MedDRA[®] system organ class (SOC), preferred term (PT), severity (mild, moderate, severe, potentially life-threatening) and whether related (definitely, probably or possibly) or not related (unrelated, unlikely) to study product. When calculating the incidence of adverse events (i.e., on a per subject basis), each subject will only be counted once per category. Per protocol, all adverse events occurring within 28 days of the third vaccination (Day 71) will be presented ([Table 18, Appendix A](#) and [Listing 10, Appendix C](#)). All events reported on the adverse event CRF will be included in the listing.

To assess safety, the number and percentage of subjects experiencing at least one AE, and the number and percentage of subjects experiencing each specific AE, categorized by body system, preferred term and product administered (for individual post-dose periods and for the entire study period) along with exact 95% CIs, will be tabulated. Overall summaries by study group include the number and percentage of subjects experiencing: (1) any adverse experience; (2) any Grade 2 or greater AE; (3) any AE judged related to study product; (4) any Grade 2 or greater AE judged related to study product; (5) Any SAE; (6) Any SAE related to IP.

Rates of all adverse events will be analyzed by Pearson's Chi-square test (or Fisher's exact test if assumptions are not met for Pearson's Chi-square), to compare groups, if applicable.

A listing of all AEs by subject will be presented ([Listing 10, Appendix C](#)).

The following summaries of adverse events will be presented by SOC, PT, study product and vaccination number:

- Total frequency of AEs ([Table 19](#) and [Table 20](#)).
- Subject level summaries of severity and relationship to study product ([Table 21](#) through [Table 28](#)).
- Listing of Grade 2 or greater non-serious AEs ([Table 29](#)).

8.4. Deaths, Serious Adverse Events and Other Significant Adverse Events

Deaths, SAEs and other significant AEs will be presented ([Table 31, Appendix A](#)), including Subject ID, Age (years), Event Description, Onset Date/End Date, Last Dose Received/Days Post Dose, Reason Reported as an SAE, Relationship to Treatment, Alternate Etiology if Not Related, Action Taken, Outcome, and Duration of Event (days). If a reasonable number of events is reported then a subject level summary will be presented.

8.5. Pregnancies

For any subjects in the Safety population who become pregnant during the study, every attempt will be made to follow them through completion of pregnancy to document the outcome, including information regarding any complications with pregnancy and/or delivery. Listings of pregnancies and outcomes will be presented ([Listing 15, Appendix C](#)).

8.6. Clinical Laboratory Evaluations

The distribution of each laboratory value will be presented by time point and treatment group ([Table 31, Appendix A](#)), including mean, standard deviation, mean change, median, median change, and range. The severity and relationship to study product of each laboratory value will be summarized separately ([Table 32, Appendix A](#)). A listing of all values in subjects will be prepared ([Listing 11](#) and [Listing 12, Appendix C](#)).

8.7. Vital Signs and Physical Evaluations

Vital sign measurements including systolic blood pressure (mmHg), diastolic blood pressure (mmHg), oral temperature (°C or °F) and heart rate (beats/minute) will be assessed at each clinic visit. Between group differences in heart rate, systolic and diastolic blood pressure will be compared using the nonparametric Kruskal-Wallis test, unless normality assumptions are fulfilled for ANOVA. Within-group changes from baseline will be assessed using the signed-rank test, unless normality assumptions are fulfilled for the paired t-test. Normality assumptions will be assessed using goodness-of-fit tests based on the empirical distribution function and by inspection of normal probability plots. Vital signs will be tabulated by visit and treatment group ([Table 33, Appendix A](#)), including mean, standard deviation, median and range and a full listing will be prepared ([Listing 13, Appendix C](#)).

A complete physical examination will occur at screening, followed by a brief physical exam about 7 days prior to the first vaccination. If the initial screening is within the day -7 window (-14 to -2), it can count as both the initial screening and pre-vaccination visit. A table summarizing the occurrence of abnormal physical exam findings will be presented by body system and treatment group ([Table 34, Appendix A](#)). A listing of physical exam values, indicating any abnormalities, will be presented ([Listing 13, Appendix C](#)).

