12.1. Description of Statistical Methods

12.1.1. Analysis Addressing the Primary Study Objective (Safety Analysis)

The primary objective of this study is safety of the Invaplex_{AR}-DETOX vaccination. All immunized subjects will be included in the safety analysis. AE data will be listed individually and summarized by system organ class and preferred terms within a system organ class for each treatment group. Serious and/or unexpected AEs will also be discussed on a case-by-case basis. For the tabulation of AEs by system organ class, a subject will be counted only once in a given system organ class. For example, a subject reporting nausea and diarrhea will be reported as one subject, but the symptoms will be listed as two separate AEs within the class. Therefore, the total number of AEs reported within a system organ class may exceed the number of subjects within the system organ class reporting AEs.

Rates of all adverse events will be analyzed by Pearson's Chi-square test (or Fisher's exact test if assumptions are not met for Pearson's Chi-square), to compare groups, if applicable. Summary tables will be created to indicate the number of subjects who experienced events. Vaccine-related events (definitely, probably, or possibly related) will be tabulated by study group. In addition, tables will be prepared to list each adverse event, the number of subjects in each treatment group

who experienced an event at least once, and the rate of subjects with adverse event(s). Adverse events will be divided into defined severity grades (mild, moderate, severe, potentially life-threatening). The tables will also divide the adverse events by relationship to the investigational product if applicable. All immunized subjects will be included in the safety analysis.

Clinical and laboratory data regarding safety, which include vital signs and safety laboratory measures, will be included in the primary analysis. Changes in pulse rate, systolic and diastolic blood pressure, weight, and respiratory rate will be compared within each group and among groups using analysis of variance procedures. For hematology and serum chemistry tests, the mean, mean change, median, median change, and range of all values for each test for each treatment group at baseline and for the final “on therapy” values will be tabulated. The tables will also divide the adverse events into those considered at least possibly related to the vaccine and those considered not related.

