4.4.5. Selection and Timing of Dose for Each Subject

This is a double-blind, placebo-controlled, dose-escalation study, with subjects randomized in a sequential manner to Cohort A (2.5 µg), B (10 µg), or C (25 µg). Within each cohort a permuted block randomization will be used to assign subjects to vaccine or placebo in a 4:1 ratio, respectively. Each subject will receive three doses at 3-week intervals (days 1, 22 and 43). Initiation of a higher dose cohort will begin only after the previous cohort has completed all 3 doses and all safety data through 7 days post-third dose have been reviewed by the PSRT.

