6. GENERAL STATISTICAL CONSIDERATIONS

6.1. General Principles

All analyses will be grouped by dose (2.5, 10, 25 µg, placebo). In general, all data will be listed, sorted by dose and subject, and when appropriate by visit number within subject. All summary tables will be structured with a column for each treatment group in order of increasing dose, with placebos pooled at the end, and will be annotated with the total population size relevant to that table, including any missing observations.

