12. SUMMARY OF CHANGES IN THE CONDUCT OF THE STUDY OR PLANNED ANALYSES

No changes have been made at this time.

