n												
Mean												
SD												
Median												
Range												
Visit 02 (1 Day post-Dose 1)												
n												
Mean												
SD												
Median												
Range												
Change from Baseline												
n												
Mean												
SD												
Median												
Range												
Continue for all other Visits (days 2, 8, 22, 23, 29, 43, 44, 50, 57, 71)												

A.3.4 Physical Exam

Table 34: Summary of Abnormal Physical Exam Findings Prior to Dose 1 – Safety Population

[figure not shown]
Body System	Visit	InvaplexAR 2.5 µg (N=X)	InvaplexAR 10 µg (N=X)	InvaplexAR 25 µg (N=X)	Placebo (N=X)
Any Abnormality	Screening				
	Day -7				
Skin	Screening				
	Day -7				
HEENT	Screening				
	Day -7				
Lymph Nodes	Screening				
	Day -7				
Respiratory	Screening				
	Day -7				
Cardiovascular	Screening				
	Day -7				
Abdomen	Screening				
	Day -7				
Neurological	Screening				
	Day -7				
Motor	Screening				
	Day -7				
Sensory	Screening				
	Day -7				
Musculoskeletal (Overall)	Screening				
	Day -7				
Musculoskeletal (Joint survey)	Screening				
	Day -7				
Other	Screening				
	Day -7				

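### SAP 8.7 as worded tests heart rate and blood pressure themselves between groups, where protocol 12.1.1 specifies change, so baseline differences between sequentially enrolled cohorts could enter the test

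*SAP*

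**What the plan says.** Protocol 12.1.1 makes vital signs part of the primary safety analysis and fixes the quantity compared: "Changes in pulse rate, systolic and diastolic blood pressure, weight, and respiratory rate will be compared within each group and among groups". The method it names is ANOVA.

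SAP 8.7 splits this into two sentences. The between-group sentence reads "Between group differences in heart rate, systolic and diastolic blood pressure will be compared using the nonparametric Kruskal-Wallis test", with ANOVA if normality holds. It names no visit and does not mention change. The next sentence does: "Within-group changes from baseline will be assessed using the signed-rank test, unless normality assumptions are fulfilled for the paired t-test".

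The Table 33 shell (SAP Appendix A.3.3) has a "Change from Baseline" block by visit and treatment group. It holds n, mean, SD, median and range, and has no p-value column. SAP 12 states: "No changes have been made at this time".

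On allocation, SAP 4.4.5 describes "subjects randomized in a sequential manner to Cohort A", then B, then C, and adds: "Within each cohort a permuted block randomization will be used to assign subjects to vaccine or placebo in a 4:1 ratio, respectively". SAP 6.1 presents the dose groups in increasing order "with placebos pooled at the end". SAP 3.3.6 defines baseline as the last value before the first vaccination, so change can be computed for every subject who has a value at both times.

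**The concern.** A programmer following SAP 8.7 would run the between-group test on the observed values at a visit. That value combines the subject's habitual heart rate or blood pressure with any effect of the injection.

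In a trial that randomised subjects to all four groups at once, the habitual part would be balanced on average. Here it need not be. Randomisation protects vaccine against placebo within a cohort, 16 against 4. It does not protect one dose against another, and it does not fully protect one dose against placebo pooled over three cohorts. If subjects enrolled later have higher or lower resting values, a level test can show a group difference that existed before the first injection, or can mask a real one.

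The within-group test does use change but has no control, so it cannot separate vaccine from time or visit effects. On this reading, the protocol's question of whether change differs among groups has no test in the SAP.

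**Working it through.** **The plan's own figures.** The documents give no figure for the vital-sign test. The only design figure, a 95% interval of 0-21% for no events in 16 subjects (SAP 5), reproduces as 1 − 0.025^(1/16) = 20.6%. It does not bear on this point.

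**Inputs from the documents.** Four analysis groups: 16, 16 and 16 on vaccine and 3 × 4 = 12 on pooled placebo. Two-sided alpha is 0.05.

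**Inputs that must be assumed.** These are the baseline drift d from cohort A to cohort C in SD units, and the correlation rho between baseline and the later visit. SDs are taken as equal at both visits. If a systolic SD of 10-12 mmHg is assumed, d = 0.5 is 5-6 mmHg and d = 1 is 10-12 mmHg.

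**Step 1: what drift does to the group means.** Let the cohort means be 0, d/2 and d at both visits, with no vaccine effect.
- Levels: the dose groups have means 0, d/2 and d. Pooled placebo has (0 + d/2 + d)/3 = d/2. This looks like a dose trend centred on placebo.
- Change: each subject's cohort shift cancels, so all four expected means are 0.

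**Step 2: false-positive rate of the four-group Kruskal-Wallis test.** Simulated with rho = 0.6 and 4,000 runs per row:

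| Drift A to C | Test on levels | Test on change |
|---|---|---|
| 0 | 4.6% | 4.2% |
| 0.25 SD | 7.5% | 4.9% |
| 0.5 SD | 15.4% | 4.7% |
| 1.0 SD | 56.8% | 4.4% |

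The level column does not depend on rho, because only the later value enters that test.

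**Step 3: precision.** Relative to a level, Var(change) = 2(1 − rho) and Var(ANCOVA) = 1 − rho². Power is for a 1 SD difference, 16 against 12. This pair is only illustrative, since the SAP plans an overall four-group test.

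| rho | Change/level variance | ANCOVA/level variance | Power: level | Power: change | Power: ANCOVA |
|---|---|---|---|---|---|
| 0.3 | 1.40 | 0.91 | 75% | 60% | 78% |
| 0.5 | 1.00 | 0.75 | 75% | 75% | 86% |
| 0.6 | 0.80 | 0.64 | 75% | 83% | 90% |
| 0.7 | 0.60 | 0.51 | 75% | 92% | 96% |
| 0.8 | 0.40 | 0.36 | 75% | 98% | 99% |

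Setting 2(1 − rho) < 1 gives rho > 0.5. Below that, change is the noisier quantity.

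**Step 4: does ANCOVA remove the drift?** Not entirely. A shift d present at both visits leaves d − rho·d = (1 − rho)d after adjustment, which is 30-40% of it at rho 0.7-0.6. In simulation at those correlations with no vaccine effect, ANCOVA rejects in about 7-8% of trials at d = 0.5 and about 12-17% at d = 1.

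**The case against.** The strongest reply is that the SAP never says raw, observed or level. Its preface presents it as elaborating the protocol's statistics, so silence on the scale need not displace the protocol's word. Table 33 also tabulates change by group. This stands in part: a test on levels is the plain reading, not an explicit statement. A reader might infer that the SAP has knowingly replaced the protocol's analysis, or that SAP 12 conceals a known departure. The documents support neither. The plain reading is still hard to avoid. The adjacent sentence in 8.7 says change when it means change, SAP 9 names both GMT and GMFR for its between-group tests, and Table 33 supplies no test.

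A second tempting reading is that testing levels must lose precision. It does not follow. Against simple change, that holds only if rho exceeds 0.5, and the documents give no rho.

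Third, drift is assumed. All cohorts share one site, one recruitment area and the same eligibility criteria, and hypertension is among the listed exclusionary health problems. With no drift, the level test keeps its nominal error rate. This stands, and it is why the 15% and 57% are conditional.

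Fourth, little depends on this test. SAP 4.2 and 5 say the trial is not designed to show group differences, and 4.2 says placebo is there mainly for blinding. Escalation rests on the stopping criteria and blinded PSRT review. The summaries listed for the PSRT in SAP 6.6 include no vital-sign test, and abnormal individual readings are graded separately. This stands and limits the importance of the point, but it does not remove the mismatch.

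**Conclusion.** The point holds in a limited form. The protocol specifies a comparison of change among groups. The SAP's between-group sentence does not, reads as a test on levels, and has no matching entry in SAP 12. Given sequential cohorts and pooled placebo, a level test is open to baseline differences between cohorts, and a test on change removes any shift that is constant over time.

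The size depends on drift that the documents do not give: no inflation at zero drift, about 15% false positives at 0.5 SD and about 57% at 1 SD, against about 5% for change. No general claim about lost precision is justified. Because the trial is not powered for group differences and escalation does not depend on this test, this is a modest correction to the reporting of a primary safety component. It does not threaten the conduct of the trial.

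**What to change.** Amend SAP 8.7 so that the between-group Kruskal-Wallis or ANOVA test is on change from baseline at named post-dose visits, as the protocol states. Print its p-value in the "Change from Baseline" block of Table 33 and keep the level summaries as description. If levels really are intended, record the departure and the reason in SAP 12.

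A baseline-adjusted ANCOVA may be added as a supportive analysis for precision, with a note that it does not fully remove a persistent cohort shift.

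The visits should be chosen deliberately. Testing all ten post-dose clinic days listed in Table 33 for three vital signs gives 3 × 10 = 30 p-values with no multiplicity adjustment (SAP 6.7), so they should be read descriptively. The same edit can state what becomes of weight and respiratory rate, which protocol 12.1.1 lists but SAP 8.7 does not compare.

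The core change costs one SAP sentence and one table column. Baseline is already defined, and heart rate and blood pressure are already collected.
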